**Table 6-1: Adverse Event Type**

AE Type	Definition
Serious Adverse Event (SAE)	AE that: 

• led to death,

• led to serious deterioration in the health of the patient, that either resulted in:

◦ a life-threatening illness or injury, or

◦ a permanent impairment of a body structure or a body function, or

◦ in-patient or prolonged hospitalization, or

◦ medical or surgical intervention to prevent life-threatening illness or injury or permanent impairment to a body structure or a body function,

• led to fetal distress, fetal death or a congenital abnormality or birth defect

Adverse Device Effect (ADE)	AE related to the use of study device.  NOTE: This definition includes adverse events resulting from insufficient or inadequate IFU, deployment, installation, operation, or any malfunction of the study device. In addition to any event resulting from use error or from intentional misuse of the study device.

Serious ADE (SADE)	ADE that has resulted in any of the consequences characteristic of a SAE.
Unanticipated SADE (USADE)	USADE which by its nature, incidence, severity or outcome has not been identified in the current version of the study protocol, IFU, or other study documentation.

## **6.1 Relationship to Device or Procedure**

The Investigator will also evaluate the relationship of the adverse event to the everlinQ endoAVF System or procedure according to the following definitions:

**Definite (YES):** The AE follows a reasonable timing from treatment (or attempted treatment) with the device and the possibilities of factors other than the device or the index procedure, such as underlying disease, concomitant drugs, or concurrent treatment can be excluded. This includes an AE that occurs during the index (endoAVF creation) procedure.

**Probable (YES):** The AE follows a reasonable timing from treatment (or attempted treatment) with the device and the probability of device or procedure involvement cannot be excluded. However, other factors such as underlying disease, concomitant medications, or concurrent treatment may be possible.

**Unlikely (NO):** The AE follows an unlikely timing relationship from treatment (or attempted treatment) or is more likely due to other factors and there is no definitive information suggesting that it was related to the device or procedure.

**Not Related (NO):** The AE has no timing relationship from treatment (or attempted treatment) or it can be explained by other factors, including underlying disease, concomitant medication, or concurrent treatment.

The Investigator will evaluate the relationship to the everlinQ device portion of the procedure using the yes/no definitions above. The everlinQ device portion of the procedure only includes insertion, deployment and removal of the everlinQ catheters.

All reported adverse events will be reviewed and adjudicated by an independent Clinical Events Committee (CEC).

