### **3.2 Risks**

Most of the potential risks and complications associated with the everlinQ endoAVF System and procedure are similar to the risks expected for Chronic Kidney Disease (CKD) patients undergoing surgically created AVF or AVG procedures. The potential risks related to the everlinQ endoAVF Systems and procedure include but are not limited to:

- Aborted or longer procedure
- Additional procedures (interventions)
- Bleeding, hematoma (a solid swelling of clotted blood within the tissues) or hemorrhage (an escape of blood from a ruptured blood vessel)
- Bruising
- Burns
- Compartment syndrome (excessive bleeding, a hematoma that worsens and causes increased pressure in a muscle compartment within the access arm)
- Death (mostly due to CKD related complications not the everlinQ endoAVF device or procedure)
- Electrocution
- Embolism (blood clot or device piece)
- Failure to mature (AVF can never be used)
- Fever (pyrogenic reaction)
- Heart problems such as arrhythmias (abnormal beats) that can be caused due to high levels of potassium in the blood (mostly due to CKD and not the everlinQ endoAVF device or procedure)
- Increased risk of congestive heart failure (heart fails due to increased flow from AVF)
- Infection (local or in the blood (bacteremia))
- Numbness, tingling and/or coolness in the fistula extremity
- Occlusion
- Problem due to sedation or anesthesia
- Pseudoaneurysm (leaking hole in artery that forms blood clot on outside of it)
- Sepsis (systemic inflammatory reaction)
- Steal syndrome or ischemia (not enough blood flow to hand)
- Stenosis
- Swelling, irritation or pain
- Thrombosis
- Toxic or allergic reaction
- Venous hypertension (arm swelling)
- Vessel, nerve or AVF damage or rupture
- Wound problem

Cannulation risks that may occur in endo AVF are similar to the cannulation risks expected for patients undergoing surgically created AVF or AVG procedures. (e.g., fistula infiltration injury due to needle cannulation, clotting, etc.)

There may also be other potential risks related to use of the everlinQ endoAVF System and procedure that are unforeseen at this time.

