**Number of Patients Who Met Functional Cannulation:** Functional Cannulation is defined as 2-needle access of the endoAVF access circuit with performance of  $\geq 2/3$ rds of  $\geq 120$  minute dialysis sessions through the endoAVF access circuit over a continuous 28-day period.

**Central Venous Catheter (CVC) Exposure:** CVC exposure will be analyzed at the follow-up time points, presenting the number/percent of patients reporting CVC use and the number/percent reporting dialysis access through other means, as well as the number/percent of subjects not yet on dialysis.

**Adverse Events:** Rate of serious procedure or device related Adverse Events (AEs) throughout the study period. The relevant events and rates of occurrence will be analyzed with a time component, to analyze procedural AEs and post-procedural AEs.

**Intervention Rate:** The percentage of patients requiring intervention will be calculated at 3, 6 and 12 months follow-up visits post index procedure. The rate of interventions that occurred during the index procedure and during short term follow-up will also be calculated.

The endoAVF-related interventions include:

- Interventions to maintain or restore patency of the endoAVF, including endovascular and surgical procedures designed to address occlusive thrombosis (resulting in absence of thrill or bruit at endoAVF) and clinically significant occlusive stenosis at or near endoAVF site.
- Interventions to support maturation of the arterialized vein segments, including endovascular procedures such as secondary coil embolization to facilitate flow into the target cannulation veins.
- Interventions to support cannulation of the arterialized vein segments, including procedures such as a superficialization or elevation where the target cannulation vein is brought closer to the skin surface to enable cannulation, without the creation of a new AV fistula.
- Any intervention to address any complications or adverse events of the access circuit.

**Note:** Any additional procedure performed at the time of the index procedure to address an adverse event will require a Post-Procedure Intervention eCRF to be completed.

**Note:** Diagnostic fistulogram, angiogram or duplex ultrasound will not be considered an intervention for the purpose of this study.

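### The relatedness categories in Section 6.1 are not mutually exclusive: one adverse event can meet both Probable (YES) and Not Related (NO), and that call decides entry to the adverse event rate

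*Combined protocol and SAP*

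**What the plan says.** Section 6.1 gives the investigator four categories.

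- **Definite (YES)** needs reasonable timing and other causes excluded. It adds: "This includes an AE that occurs during the index (endoAVF creation) procedure".
- **Probable (YES)** needs reasonable timing and that "the probability of device or procedure involvement cannot be excluded". It continues: "However, other factors such as underlying disease, concomitant medications, or concurrent treatment may be possible".
- **Unlikely (NO)** is met by unlikely timing, or when the event "is more likely due to other factors and there is no definitive information suggesting that it was related to the device or procedure".
- The test for **Not Related (NO)** reads: "The AE has no timing relationship from treatment (or attempted treatment) or it can be explained by other factors, including underlying disease", followed by medication and concurrent treatment.

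The same YES/NO definitions are then used for a separate judgement on the device portion of the procedure, which covers only insertion, deployment and removal of the catheters. Sections 6.1 and 8.3 say that an independent CEC reviews and adjudicates the adverse events, without stating criteria.

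The Adverse Events outcome in Section 4.3 is the "Rate of serious procedure or device related Adverse Events (AEs) throughout the study period". Table 6-1 makes an event an adverse device effect if it is related to use of the device. Table 8-1 sends serious adverse device effects (SADEs) to the sponsor and the ethics committee (EC), and serious adverse events (SAEs) to the sponsor.

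**The concern.** Categories that collapse to YES or NO should give one answer per event. Here two assessors can each follow the text exactly and reach opposite answers on the same event.

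Two things depend on the answer. The first is the numerator of the Section 4.3 rate, which admits only serious events judged related to procedure or device. Section 7 plans no hypothesis tests, so the reported rate is itself the result, and Section 4.2 foresees its use for reimbursement and publication. The second is the reporting route: through the device-portion judgement, the same definitions decide whether a serious event goes to the sponsor and EC as a SADE or to the sponsor as an SAE.

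**Working it through.** The documents give no figure to reproduce, so the definitions are compared first and the possible effect on the rate is illustrated second.

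**1. Probable against Not Related.** Take an event with reasonable timing, involvement that cannot be excluded, and underlying disease as a possible explanation.

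- Probable: timing is met, non-exclusion is met, and the other possible cause is expressly tolerated. Result: YES.
- Not Related: the first limb fails because there is a timing relationship. The second limb, joined by *or*, asks only that "it can be explained by other factors, including underlying disease, concomitant medication, or concurrent treatment". It is met. Result: NO.

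**2. Probable against Unlikely.** If another cause is also the more likely one and there is no definitive information of relatedness, the second limb of Unlikely is met whatever the timing. The event is both YES and NO.

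**3. Definite against Not Related.** An event during the index procedure is assigned to Definite. If another factor can explain it, it also literally meets Not Related.

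**4. Enumeration.** Each definition was written as a logical condition on seven attributes: timing (reasonable, unlikely, none); other causes excludable; involvement excludable; explainable by other factors; more likely due to other factors; definitive information of relatedness; intra-procedural. Incoherent combinations were dropped, for example other causes excluded yet explaining the event. This leaves 11 combinations of the five middle attributes and 4 settings of timing with procedure (reasonable timing inside or outside the procedure, unlikely, none), so 11 × 4 = 44 profiles.

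| Overlap | Current text | With Not Related tightened as under the fix |
|---|---|---|
| Probable and Not Related | 8 (4 not intra-procedural) | 0 |
| Probable and Unlikely | 2 | 2 |
| Definite (intra-procedural rule) and Not Related | 6 | 2 |
| At least one YES and one NO category | 10 | 4 |

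Rows share profiles, so they do not add up. The counts show that overlap exists; they are not event frequencies. The 4 left in the last column are settled by a precedence sentence.

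**5. Illustration of size.** The denominator is the planned maximum of 200 (Section 4.1). The number S of patients with a serious event that could count as related, and the share a of them in the overlap, are assumptions. The rate is S/200 if overlaps are YES and S(1 − a)/200 if they are NO. Intervals are Clopper-Pearson 95%.

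| S | Overlaps YES | Overlaps NO, a = 20% | Overlaps NO, a = 50% |
|---|---|---|---|
| 10 | 10/200 = 5.0% | 8/200 = 4.0% | 5/200 = 2.5% |
| 20 | 20/200 = 10.0% (6.2 to 15.0) | 16/200 = 8.0% (4.6 to 12.7) | 10/200 = 5.0% (2.4 to 9.0) |
| 30 | 30/200 = 15.0% | 24/200 = 12.0% | 15/200 = 7.5% |

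Each NO column assumes that every overlapping event is scored the same way, so the pairs are extremes.

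**The case against.** **The scale is graded.** Probable speaks of other causes being possible, Not Related of the event being explained by them. A sensible assessor may read the latter as fully explained, which narrows the overlap. That is a plausible intention, but the text does not state it.

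**The CEC settles it.** Independent review of every reported event may well make the calls more consistent. It does not make the definitions exclusive: no separate criteria or tie-break are given, and the plan does not say whether the investigator's or the CEC's classification is analysed.

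**There is a partial precedence rule.** The intra-procedural sentence places those events in Definite, and its intent is clear. It does not reach events after the procedure, where 4 of the 8 Probable/Not Related profiles lie.

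**The pool is small.** Section 6 collects only events tied to the index procedure, device, access site or fistula, so most general morbidity of kidney disease never reaches Section 6.1. This stands and limits the size of the problem.

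**A reader might infer that almost any listed risk can be put down to kidney disease.** Section 3.2 does not support this. It makes that attribution for death ("mostly due to CKD related complications not the everlinQ endoAVF device or procedure") and for arrhythmia-type heart problems only. It ties congestive heart failure to fistula flow, and many other entries are procedural or access-related.

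**A reader might infer that the YES/NO call as a whole fixes the reporting route.** It does not. A procedure-related event is not a SADE for that reason alone; only the device-portion judgement matters there.

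**Conclusion.** The point holds as a wording defect that gives contradictory classifications: Probable overlaps with Not Related and, more narrowly, with Unlikely, and the intra-procedural part of Definite overlaps with Not Related. The rate in Section 4.3 is not uniquely defined for events in the overlap, and the SADE/SAE distinction inherits the ambiguity through the device-portion judgement.

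The size is unknown. The shift from 10.0% to between 8.0% and 5.0% rests on assumed counts and uniform scoring. A reader might infer that the rate will be biased low; the documents do not establish a direction, because the literal text permits YES as readily as NO. Nor is this rate the study's only information on complications. The Intervention Rate in Section 4.3 includes interventions for complications of the access circuit and does not use the relatedness categories. The change should be made, since it removes a contradiction at little cost.

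**What to change.** 1. Redefine Not Related as: *no timing relationship, or the event is explained by other factors and device and procedure involvement can be excluded*.
2. Add: *If an event meets more than one category, the most related category applies.*
3. State that the CEC applies the same definitions and that the CEC classification is the one analysed.

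Leave the *or* in Unlikely as it is. Requiring both unlikely timing and a more likely other cause would leave an event with unlikely timing and no identified other cause in no category; the precedence sentence already resolves the overlap with Probable. It would help to make clear that the condition about definitive information belongs to the second limb of Unlikely only. Otherwise an event with unlikely timing, another possible explanation and definitive information of relatedness would have no category once Not Related is tightened.

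The cost is wording in the protocol and in any CEC instructions. The reported related-event rate may be higher, because doubtful events would count as related.

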## **7 DATA ANALYSIS**

The study will be observational in nature and will not involve the formulation or statistical testing of study hypotheses.

Variables that are categorical in nature (such as gender) will be summarized by frequencies and percentages while those that are continuous in nature (such as age) will be summarized by the mean, standard deviation, minimum and maximum values. Continuous variables that appear not to be normal in distribution will also be described by the median value.

Variables involving time (such as primary patency) will be analyzed using the Kaplan-Meier product limit approach. This approach yields cumulative probabilities of having an endoAVF for a given period of time without the occurrence of some specified terminal event, such as endoAVF thrombosis. The analysis requires both a time variable and a variable indicating whether or not the event of interest has occurred. Results of these analyses will be presented both graphically and in tabular form.

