Intervention Rate	
Rate of all interventions (and specific interventions) will be reported. All interventions that occur during the index procedure and during follow-up will be reported.
 
 
Interventions to maintain or restore patency of the endoAVF, including endovascular and surgical procedures designed to address occlusive thrombosis (resulting in absence of thrill or bruit at endoAVF) and clinically significant occlusive stenosis at or near endoAVF site.
 
Interventions to support maturation of the arterialized vein segments, including endovascular procedures such as secondary coil embolization to facilitate flow into the target cannulation veins.
 
Interventions to support cannulation of the arterialized vein segments, including procedures such as a superficialization or elevation where the target cannulation vein is brought closer to the skin surface to enable cannulation, without the creation of a new AV fistula.
 
Any intervention to address any complications or adverse events of the access circuit.
 

Maturation of endoAVF	Successful hemodialysis using 2- needle cannulation OR Vascular accesses that is free of stenosis or thrombosis, with brachial artery flow of at least 500 ml/min and at least a 4.0 mm vein diameter as measured via duplex ultrasound.
Maturation time	The number of days between the date of AVF creation and the date of endoAVF maturation (based on primary efficacy endpoint definition of maturation).
Occlusion	The blockage of a blood vessel.
Operator	Person who conducts index procedure.
Pre-dialysis Patient	Patient who was not receiving dialysis at the time of enrollment.
Primary patency	The interval from the time of access placement until any intervention designed to maintain or re-establish patency, access thrombosis, access abandonment, or the time of measurement of patency.
Procedure duration	The sum of the venography time, endoAVF creation time, coil and closure time.
Protocol deviation	Deviation from the approved Study Protocol.
Secondary Patency	The interval from the time of access placement until access abandonment, loss to thrombosis, or the time of patency measurement including intervening manipulations (surgical or endovascular interventions) designed to re-establish functionality in thrombosed access.
Stenosis	The abnormal narrowing of the blood vessel.

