## **4.3 Study Outcome Measures**

All patients enrolled in the study and do not have a renal transplant, will be included in these outcome measurements unless otherwise noted.

**Primary Patency:** The interval from the time of access placement until any intervention designed to maintain or re-establish patency, access thrombosis, access abandonment, or the time of measurement of patency.

❖ **endoAVF abandonment definition:**

The endoAVF is considered abandoned if any of the following occur:

- The endoAVF is occluded and patency cannot be restored by any intervention, including medical, surgical, radiological or rest through the last follow up;
- The endoAVF is deemed inadequate for dialysis (for example, it never matures or is too deep for needle access) and the associated problem cannot be corrected by any intervention, including medical, surgical, radiological or rest;
- The endoAVF is ligated.

An endoAVF is not considered abandoned when it is not cannulated in subjects with a successful renal transplantation or when reasons of subject preference alone preclude cannulation.

**Assisted Primary Patency:** The interval from access placement to thrombosis or abandonment; not triggered by access circuit interventions performed in the absence of occlusion.

**Secondary Patency:** The interval from the time of access placement until access abandonment, loss to thrombosis, or the time of patency measurement including intervening manipulations (surgical or endovascular interventions) designed to re-establish functionality in thrombosed access.

**Functional Patency:** The interval of time from the first 2-needle dialysis utilizing the access until access abandonment.

**Procedure Success:** The successful creation of an endoAVF with blood flow confirmed intraoperatively by fistulography or by duplex ultrasound postoperatively.

**Time to Endovascular Fistula (endoAVF) Maturation (Vascular Access Usability):** Total time (number of days) from successful endoAVF creation to one of the following:

- Successful hemodialysis using 2 needle cannulation ***OR***
- Vascular accesses that is free of stenosis or thrombosis, with brachial artery flow of at least 500 ml/min and at least a 4.0 mm vein diameter as measured via duplex ultrasound.

**Time to Cannulation:** The time (number of days) from the index procedure (successful endoAVF creation) to the first use of the endoAVF for cannulation will be reported.

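### Neither summary that Section 7 allows for time to maturation and time to cannulation accounts for fistulas that fail first

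*Combined protocol and SAP*

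**What the plan says.** Section 7 (Data Analysis) offers two summaries that could apply to a time outcome. The first is Kaplan-Meier: "Variables involving time (such as primary patency) will be analyzed using the Kaplan-Meier product limit approach". The section adds: "The analysis requires both a time variable and a variable indicating whether or not the event of interest has occurred". That is a two-state indicator, with no third state for an event that rules out the one of interest. The second is the rule for continuous variables (mean, standard deviation, minimum, maximum), with the addition "Continuous variables that appear not to be normal in distribution will also be described by the median value".

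Two outcomes measure time to a success. Section 4.3 defines time to maturation as "Total time (number of days) from successful endoAVF creation to one of the following" (2-needle dialysis, or a flow and diameter criterion). It defines time to cannulation as follows: "The time (number of days) from the index procedure (successful endoAVF creation) to the first use of the endoAVF for cannulation will be reported". The definitions table describes maturation time as "The number of days between the date of AVF creation and the date of endoAVF maturation". No method is named for either outcome specifically.

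Two further provisions matter. Abandonment in Section 4.3 includes this case, where the problem cannot be corrected: "The endoAVF is deemed inadequate for dialysis (for example, it never matures or is too deep for needle access". Under Table 5-2 participation ends at permanent loss or abandonment, and Section 5.8 lists both abandonment and death as study exits.

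**The concern.** Kaplan-Meier suits the patency outcomes, where abandonment is itself an event. For maturation and cannulation, abandonment and death make the event impossible. A patient who leaves for either reason has a time, no event and no later follow-up. With one yes/no indicator, Kaplan-Meier treats that patient as still able to mature and spreads the lost weight over those who remain.

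The other route has the opposite gap. A number of days to maturation exists only for fistulas that matured, so failures drop out of the mean or median.

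No hypothesis is tested, so what is at stake is a descriptive figure. It still matters: Section 3.1 suggests that maturation may improve on historical data, and Section 4.2 says the data may support reimbursement and publications. A maturation figure that is biased upward, or blind to failures, is a poor basis for either.

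**Working it through.** The plan states no expected maturation rate, so there is no figure of its own to reproduce.

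**Inputs from the documents.** Up to 200 treated patients and 12 months of follow-up (Section 4.1). Surgical fistulas mature over 1-3 months, and 28-60% fail to mature (Section 1). Patients not yet on dialysis are expected to start within 3 months (Section 4.5.1).

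**Assumptions.** Maturation uniform on days 30-90; deaths 5%, uniform on days 1-365; 5% unresolved at 12 months; 10-25% abandoned, uniform over the windows shown below.

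**Kaplan-Meier route.** Let M(t), A(t) and D(t) be the shares of all created fistulas that have matured, been abandoned, or ended in death by day t, and let S = 1 − M − A − D.

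- Cumulative incidence of maturation: M(t).
- One minus Kaplan-Meier, with failures and deaths censored: 1 − exp(−∫ dM(u)/S(u)).

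Because S ≤ 1 − M, the second is never below the first. If every failure and death follows the last maturation, S = 1 − M while maturation is under way, and the two are equal.

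Overstatement at 12 months, in percentage points:

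| Matured / abandoned / died (%) | Abandonment days 90-365 | Abandonment days 45-270 | Days 45-270, deaths only after day 90 |
|---|---|---|---|
| 80 / 10 / 5 | 0.8 | 2.0 | 1.1 |
| 70 / 20 / 5 | 0.7 | 2.5 | 1.8 |
| 65 / 25 / 5 | 0.6 | 2.7 | 2.0 |

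In the 90-365 column maturation is over before any abandonment, so the whole gap comes from the assumed early deaths. Moving the deaths to after day 90 makes it 0.0. At 60% non-maturation (40/50/5) the gaps are under 0.5 points (90-365) and 2.5 points (45-270). The median moves by about 0-1 day. For scale, the 95% half-width at 70% with n = 200 is 1.96 × √(0.7 × 0.3 / 200) = 6.4 points.

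For cannulation, take the later of maturation and dialysis start (days 0-90 in 0%, 50% or 100% of patients) plus a 0-14 day lag. Simulation gives gaps of about 0.8-1.0 points (abandonment 90-365) and 2.4-3.8 points (45-270).

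**Sensitivity to timing.**

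- Abandonment on days 30-180: 3.5-5.7 points.
- Maturation to day 180 with abandonment on days 45-270: about 6-9 points.
- Maturation to day 180 with abandonment on days 30-120: about 11-23 points.
- Constant hazards over 12 months, with shares M matured and F abandoned and no separate deaths: one minus Kaplan-Meier = 1 − (1 − F − M)^(M/(F+M)). For F = 0.10, M = 0.80 this is 1 − 0.10^0.889 = 87.1%, against 80.0%. For F = 0.60, M = 0.35 it is 1 − 0.05^0.368 = 66.8%, against 35.0%. The gaps are about 7 and 32 points.

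**Mean or median route.** Among matured fistulas only, the median is the midpoint of days 30-90, which is 60 days, whatever share p matures. The day by which half of all created fistulas have matured is 30 + 60 × 0.5/p.

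| Share matured, p | Left out of 200 | Median, matured only | Day half of all have matured |
|---|---|---|---|
| 0.80 | 40 | 60 | 67.5 |
| 0.72 | 56 | 60 | 71.7 |
| 0.65 | 70 | 60 | 76.2 |
| 0.40 | 120 | 60 | not reached |

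**The case against.** The best reply is that Section 7 may not mean Kaplan-Meier for these outcomes at all. It describes the method as giving the probability of having a fistula "without the occurrence of some specified terminal event, such as endoAVF thrombosis", and its example is primary patency. Maturation and cannulation are not terminal events, and both are defined as a number of days. This stands: the reading is open. It does not rescue the plan, because the alternative leaves the failures out.

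Second, a reader might infer that the plan states that failed fistulas are censored. It does not. Censoring is inferred from the yes/no indicator together with exit at abandonment or death. An analyst who kept failures at risk as non-events to 12 months would avoid the bias, but the text does not say to do so. The abandonment definition also requires that the problem cannot be corrected by any intervention or rest, which points to late declaration and a smaller gap.

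Third, days to maturation among matured fistulas is a legitimate description. That is true if the number that did not mature is shown beside it, which the plan does not require.

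Fourth, a reader might infer that the report would hide failures. It would not: abandonment ends every patency interval, and the number meeting functional cannulation is reported.

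**Conclusion.** The point holds as a minor one. Both summaries that Section 7 allows for these two outcomes mishandle fistulas that fail first: one can overstate the share succeeding and never understates it, and the other ignores the failures.

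No size follows from the documents, which give neither abandonment times nor death rates. Under the main assumed timings the overstatement of 12-month maturation runs from 0 to 2.7 points, below the sampling half-width of 6.4 points. Part of it is due to assumed deaths and not to failed fistulas: with abandonment on days 45-270, 1.1-2.0 of the 2.0-2.7 points remain once early deaths are removed. A reader might take the 7 to 32 points under constant hazards as the expected bias. The documents do not support that, since it rests on assumed timing, as the smaller figures do. Only the direction is certain. No test, sample size, patency outcome or functional cannulation count is affected.

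**What to change.** Keep Kaplan-Meier for the patency outcomes and add to Section 7:

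> Time to maturation and time to cannulation will be summarized by the cumulative incidence (Aalen-Johansen) with 95% CIs at 1, 3, 6 and 12 months among patients with successful endoAVF creation. Abandonment (including ligation) and death before the event are competing events. Renal transplant before the event is also a competing event, and patients are not removed because of a later transplant. Patients are otherwise censored at withdrawal, loss to follow-up or end of study. Any mean or median among fistulas that reached the event will be shown with the number that did not.

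The transplant sentence is needed because Section 4.3 leaves transplanted patients out of the outcome measures unless noted otherwise, which excludes on a later event.

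A simpler acceptable option is the proportion reaching the event by each visit, with abandoned and deceased patients kept in the denominator as non-events.

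The cost is a few sentences and standard software. Section 5.8 already has exit reasons recorded on the End of Study eCRF; the dates of abandonment, death and transplant must be confirmed as captured. The reported maturation percentage may be slightly less favourable.
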